## Monitoring and evaluation

Table 6 describes the outcome variables. The conceptual framework of obesity causes (Figure 1) specifies a wide variety of factors that influence this pathology's immediate causes. To modify these factors, it is necessary to implement strategies that will impact the outcome variables, but whose impact is not direct. These strategies are mainly oriented towards modifying the food supply, increasing opportunities to make physical activity,

creating healthy environments, and community participation, among others; not precisely modifying the body composition. Many of the strategies proposed for the project will reflect on the outcome variables; however, their monitoring during the intervention will be given through process indicators, among which stand out:

- Number of parent's reunions, for each topic of health and nutrition
- Number and percentage of parents that assist the reunions about topics of health and nutrition (total of parents per group/number of parents that assist per group)
- Number of events outside school hours realized with health and nutrition topics
- Number of sports events realized
- Number of assistants and participants on sports events and health and nutrition topics
- Effective classes of physical education per group (physical education classes programmed per group / physical education classes realized per group)
- Duration pf physical education classes (minutes)
- Application grade of the guidelines
- Number of non-recommended foods present at the school campus

These are some of the indicators proposed; however, with the formative and viability investigation results, it will be possible to propose various actions for which indicators of the specific process will be designed.

During the implementation of the strategies, detailed records will be kept of relevant related events that may affect food and physical education dynamics in the schools and the locality (Table 4), both in the intervention and control localities. Similarly, a detailed registry will be kept of the agreements reached in meetings with key actors and the support given by the municipality and school authorities.

*Table 6 Outcome variables*

Category			
Basic causes			Underlying causes
Diet	Physical activity	Interpersonal factors	Environment
Energy consumption	Number of steps	Beliefs	Availability and accessibility of food and beverages
Fat consumption	Speed	Knowledge	Quality of infrastructure for physical activity and meals

Recommended and non-recommended food consumption	Resilience	Attitudes	Length and quality of physical education classes
Beverage consumption	Strength	Motivation, intention to change	Policies to regulate the sale and consumption of food
Local foods consumption		Social empowerment	

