## Proposed methods

The project will have a total duration of 3 years (figure 2). The outcome variables will be the change in consumption and availability of food and drinks, time spent on physical activity within school settings, knowledge, and attitudes regarding the consumption of healthy food, water, and realization of physical activity, as well as the empowerment of community actors involved about their health. On the other hand, it is expected to find serum lipids and glucose modifications in the prevalence of children's overweight and obesity and physical abilities (endurance, strength, and speed). Finally, it is intended that the present project establishes a background of the need to maintain a permanent health promoter in all schools of primary education.

The strategies will be carried out on a community and school level. The proposed actions will be developed at three local elementary public schools during the morning shift; meanwhile, the other three, belonging to the municipality of Villa Corona, Jalisco, will only be evaluated (control group). Table 1 presents the general characteristics of the intervention and control schools.

[figure not shown]

Figure 2 Study design in Acatlán de Juárez, Jalisco

Table 1. General characteristics of elementary schools in the intervention and control group

School	Municipality	Type	schedule	students	teachers	groups
David G. Berlanga	Acatlán	Intervention	8:00 to 12:30	571	19	18
Cuauhtémoc	Acatlán	Intervention	8:00 to 12:30	238	9	9
Justo Sierra	Acatlán	Intervention	8:00 to 12:30	353	12	12
Benito Juárez	Villa Corona	Control	8:00 to 12:30	380	12	12
Roberto Quiroz Guerra	Villa Corona	Control	8:00 to 12:30	277	9	9
Manuel López Cotilla	Villa Corona	Control	8:00 to 12:30	251	9	9

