## Information analysis plan

It is pretended to analyze the information in 3 different sections. One section with impact results, one section with process results, and one section with qualitative results.

The section with impact results will present central tendency measures and dispersion of the information obtained during the measurement periods, having as main outcome variables:

- Score in beliefs, attitudes, and knowledge questionnaires.
- The average consumption of energy and fat
- Consumption of healthy foods (recommended)
- Consumption of non-healthy foods (Not recommended)
- Number of steps during the day
- Availability of healthy foods and non-healthy foods at school
- Availability of drinking water at schools
- Number and quality of spaces to develop physical activity
- Score in endurance, speed, and strength test

As for the process results section, six-month reports will be elaborated and delivered to the financing company, presenting information on the process indicators mentioned in the previous section; as well as the summary of the activities and relevant events that have taken place in the community and the agreements reached with the key actors.

The section on qualitative results will be presented once the formative research has concluded, and after each measurement phase. This section will present the barriers and

possible solutions to improve eating habits and encourage physical activity in the population provided by the key actors and elements of the actors' perception of the intervention's progress and satisfaction.

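### Two process indicators (parent attendance and physical education classes delivered) have numerator and denominator reversed, so their values rise as delivery falls

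*Protocol*

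**What the plan says.** The Monitoring and evaluation section of the protocol explains that many strategies act only indirectly on the outcome variables, and that "their monitoring during the intervention will be given through process indicators". It then lists the indicators. Two of them carry a formula:

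- Parent attendance is labelled "Number and percentage of parents that assist the reunions about topics of health and nutrition", and the formula in brackets is "total of parents per group/number of parents that assist per group".
- Class delivery is given as "Effective classes of physical education per group (physical education classes programmed per group / physical education classes realized per group", where the bracket is the formula.

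The Information analysis plan makes process results one of three analysis sections and states that "six-month reports will be elaborated and delivered to the financing company, presenting information on the process indicators mentioned in the previous section". No other part of the protocol gives either ratio the other way round.

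**The concern.** In both formulas the whole or planned count is on top and the achieved count is underneath. The parent indicator therefore contradicts its own label: a percentage of parents attending must lie between 0% and 100%, and the formula cannot give a value below 100%. The class indicator runs against its name, since a larger value means that fewer of the planned classes took place.

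At stake is the description of how well the intervention was delivered. The general objective covers functionality as well as effect, and these indicators are how the protocol tracks delivery. A reader of a six-month report would take a rising value as improvement when it means the reverse. The groups with the poorest delivery, which monitoring most needs to find, would show the highest values or none at all.

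**Working it through.** **Inputs.** The two formulas and labels come from Monitoring and evaluation. Group size comes from Table 1 ("Table 1. General characteristics of elementary schools in the intervention and control group"). The protocol states no value for either indicator, so there is no figure to reproduce.

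**Group size.**
- Intervention: 571 + 238 + 353 = 1162 students in 18 + 9 + 12 = 39 groups, or 29.8 per group.
- Control: 380 + 277 + 251 = 908 students in 12 + 9 + 9 = 30 groups, or 30.3 per group.
- Together: 2070 / 69 = 30.0 per group.

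I assume one parent per child, so T = 30 parents per group. This only makes the example concrete. The result depends on the share attending, a/T, so counting two parents per child changes nothing.

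**Parent attendance.** As written: 100 × T/a. As labelled: 100 × a/T. The attendance levels are illustrative.

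| Attending (a) of 30 | As written | As labelled |
|---|---|---|
| 30 | 100% | 100% |
| 15 | 200% | 50% |
| 10 | 300% | 33.3% |
| 3 | 1000% | 10% |
| 0 | undefined | 0% |

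Because a ≤ T, T/a is never below 1, and for fixed T it rises as a falls. The direction holds for any group size.

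**Physical education classes.** As written: P/r (programmed over realized). Reversed: r/P. I assume P = 8 programmed classes for illustration.

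| Realized (r) of 8 | As written | Reversed |
|---|---|---|
| 8 | 1.00 | 1.00 |
| 6 | 1.33 | 0.75 |
| 4 | 2.00 | 0.50 |
| 0 | undefined | 0 |

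**Averaging over groups.** The protocol defines the ratios per group and does not say how groups are combined; a simple mean is my assumption. Take two groups of 30 with 30 and 3 parents attending. The mean of the labelled percentages is (100% + 10%)/2 = 55%. The mean of the values as written is (100% + 1000%)/2 = 550%, and its reciprocal is 1/5.5 = 18%. A single group's value can be inverted back, but an average of such values cannot. One group with no attendance leaves the average undefined.

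**The case against.** Several points on the other side are fair.

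- **The label settles the intent.** The text reads as a translation, the slash may only pair the two counts, and a value such as 200% would expose itself as impossible. Staff may well calculate it correctly. This is possible, but the bracket is the only definition the protocol gives, and it conflicts with the label.
- **The two cases are not equal.** The class indicator is not called a percentage and has no stated direction or target. Programmed over realized is a usable, if awkward, ratio. This stands: the contradiction is firm for parents, while for classes it rests on the name of the indicator.
- **Little information is lost.** The number of attending parents is reported alongside the percentage, class duration is a separate indicator, Table 5 has each group's weekly classes monitored, and SOFIT covers class quality. If both counts are shown, a single value can be inverted. This limits the harm, but does not help once values have been averaged over groups.
- **Nothing inferential depends on it.** No test, threshold, sample size or main impact outcome uses these ratios, and the list is described as a proposal. This also stands, although the Information analysis plan commits to reporting the listed indicators.

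The point is not a detail left for a statistical analysis plan, because the protocol itself states the formulas.

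**Conclusion.** The concern holds. The parent-attendance formula is the reciprocal of what its label promises and cannot fall below 100%. The class formula rises as fewer classes are held, against the sense of its name. Both are undefined at zero delivery. For a group with half its parents present, the value is 200% instead of 50%; with one parent in ten, 1000% instead of 10%. The direction needs no assumption; only the group of 30, the attendance levels and the 8 classes are illustrative. The reports would be misstated only if the formulas are applied as written. The correction should be made, but it bears on the description of implementation and not on the trial's main impact results.

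**What to change.** In Monitoring and evaluation, restate the two formulas:

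- Parent attendance (%) = parents attending / total parents in the group × 100.
- Physical education delivery = classes realized / classes programmed, per group.

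Show numerator and denominator for each group in the process results and six-month reports, so that zero delivery appears as zero and any pooled figure can be checked.

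The cost is rewording two brackets. Both counts in each ratio are already needed for the present formulas, so no extra data are collected.

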## Information analysis plan

It is pretended to analyze the information in 3 different sections. One section with impact results, one section with process results, and one section with qualitative results.

The section with impact results will present central tendency measures and dispersion of the information obtained during the measurement periods, having as main outcome variables:

- Score in beliefs, attitudes, and knowledge questionnaires.
- The average consumption of energy and fat
- Consumption of healthy foods (recommended)
- Consumption of non-healthy foods (Not recommended)
- Number of steps during the day
- Availability of healthy foods and non-healthy foods at school
- Availability of drinking water at schools
- Number and quality of spaces to develop physical activity
- Score in endurance, speed, and strength test

As for the process results section, six-month reports will be elaborated and delivered to the financing company, presenting information on the process indicators mentioned in the previous section; as well as the summary of the activities and relevant events that have taken place in the community and the agreements reached with the key actors.

The section on qualitative results will be presented once the formative research has concluded, and after each measurement phase. This section will present the barriers and

possible solutions to improve eating habits and encourage physical activity in the population provided by the key actors and elements of the actors' perception of the intervention's progress and satisfaction.

## Ethical aspects

Parent meetings will be held at the intervention and comparison sites for each grade at each school to explain the project and request oral consent from children's parents who have not been selected in the sub-sample, to obtain measurements of weight, waist, neck, basic folds, and height. Copies of the designed informed consent letter will be made available upon request. Different informed consent letters will be read to parents of children in the intervention community and the control locality. In addition, a written informed consent letter will be requested from the parents of the children selected to take the additional measurements (Appendix 1). The signing of the consent letters will be realized at smaller meetings and/or home visits to obtain their contentment regarding the collection of blood samples and questionnaires of diet and physical activity in children, blood pressure measurements, and step counts. The assent of all children over 7 years of age will be obtained with an informed assent letter (Appendix 2). Both letters of consent and assent will be read and explained to participants to ensure that they have understood their content. These letters are written specifically for the intervention and comparison locality.

Participating key actors will be asked for informed consent to participate in interviews and will be provided with a copy of the contact information from the researchers responsible for the project (Appendix 3).

Reunions will be carried out with different community groups, the school community, and the decision-makers separately to present the results after each measurement period. The reunion will help maintain the community involved in the process, as well as receive feedback. Parents will be given the results of their children's nutritional state, blood pressure, glucose, cholesterol, triglyceride levels, and the results of the physical abilities test. In the case of detecting that any child requires medical attention, it will be referred to Acatlán Health Services for treatment. If the found condition is severe, the kid will have a secured place for its special treatment at the New Civilian Hospital of Guadalajara "Juan I. Menchaca" in Guadalajara Jalisco.

## Schedule

The intervention is scheduled to begin in September 2015; however, in June and July of 2015, the formative research and the viability study will be carried out within the schools. It is contemplated a training period for staff before each of the 3 periods of evaluation. The total duration is 3 years (2015-2018), with the last field evaluation scheduled at the end of the 2017-2018 school year. There is also a 6-month period for data analysis and the elaboration of the final report at the end of the project. Table 7 describes the estimated times on which each of the project periods will be developed.

Year	Month	Activities	School year
2015	April	Measurement of non-participating schools in the intervention location	2014-2015
	June-July	Formative research and viability study	
	July- August	Analysis of formative research and staff training	
	August	Planning of intervention strategies	
	September	Presentation of strategies before a group of experts and corrections. Preparation of material for initial evaluation	2015-2016
	October – November	Baseline evaluation	
	November	Opening event	
	December	Formative research article School vacations	
2016	January – July	Baseline measurement article Strategy implementation	2016-2017
	Easter	School vacation	
	July – August	School vacation	
	July – August	Staff training	
	September – October	Intermediate measurement	
	November – December	Strategy implementation	
	December	School vacation	
2017	January – March	Intermediate measurement article Implementation of strategies	2016-2017
	Easter	School vacation	
	April – July	Implementation of strategies	
	July – August	School vacation	
	September – December	Implementation of strategies	
	December	School vacation	
2018	January – April	Implementation of strategies	2017-2018
	Easter	School vacation	
	March – April	Implementation of strategies Staff training	
	May – June	Final evaluation	
	July - December	Analysis of information	
2019	January	Final report evaluation Final evaluation article	2019

## Budget

Table 8 describes the different items considered for the budget per year, which considers the necessary costs for developing all the stages of the project, including from staff training, to the end of the collection and analysis of the information. The work team includes a project coordinator, who will be in charge, along with the operative responsible for the quality of the information and the development of the fieldwork. A coordinator for the qualitative component is also included. There will be an additional person who will support the qualitative research. The team will have 2 social service providers in charge of collecting quantitative information during the different stages, as well as implementing and evaluating the intervention.

Due to the type of methodology used in this study, the totality of strategies to be implemented during the intervention is unknown; however, previous experience of INSP groups in similar interventions indicate that it will be necessary to develop materials and campaigns to promote the consumption of fruits and vegetables, as well as the creation of healthy spaces within the school. All materials and equipment for the design of an educational campaign are included, including the ones that will need reproduction and the materials for its implementations.

On the other hand, expenses for transportation (gasoline) and travel of personnel in charge of collecting information and implementing strategies are included in the items of transportation and travel expenses, respectively. Finally, the administrative cost of the projects is included in the budget, which represents 15% of the total cost of the intervention, requested by ITESO's administration.

	2015	2016		2017		2018	TOTAL
	May	January	July	January	July	January	
PERSONNEL/STAFF	\$132,000.00	\$237,000.00	\$222,000.00	\$174,000.00	\$174,000.00	\$249,000.00	\$1,188,000.00
TRANSPORTATION	\$7,000.00	\$12,500.00	\$9,000.00	\$9,000.00	\$9,000.00	\$7,500.00	\$54,000.00
TRAVEL EXPENSES	\$6,000.00						\$6,000.00
BIOCHEMICAL DETERMINATIONS	\$105,000.00		\$105,000.00			\$105,000.00	\$315,000.00
MATERIAL & EQUIPMENT	\$16,200.00	\$88,420.00	\$3,600.00	\$15,000.00	\$3,600.00	\$15,000.00	\$141,820.00
OTHER EXPENSES		\$15,000.00				\$15,000.00	\$30,000.00
STATIONERY AND OTHERS		\$10,000.00	\$10,000.00	\$10,000.00	\$10,000.00	\$10,000.00	\$50,000.00
EVENTS	\$15,000.00					\$10,000.00	\$25,000.00
SUBTOTAL	\$281,200.00	\$362,920.00	\$349,600.00	\$208,000.00	\$196,600.00	\$411,500.00	\$1,809,820.00
ADMINISTRATIVES ITESO	\$49,623.53	\$64,044.71	\$61,694.12	\$36,705.88	\$34,694.12	\$72,617.65	\$319,380.00
15% (OVERHEAD)							
TOTAL IN PESOS	\$330,823.53	\$426,964.71	\$411,294.12	\$244,705.88	\$231,294.12	\$484,117.65	\$2,129,200.00
TOTAL IN DOLLARS	\$21,505.23	\$27,754.90	\$26,736.23	\$15,907.14	\$15,035.31	\$31,470.13	\$138,408.93

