## Fieldwork logistics in evaluation periods

The field strategy for information gathering in the three evaluation periods will be organized with a single brigade of six people (during the evaluation periods, there will be two more people to complement the 6-member brigade and facilitate the collection of information; while four members will stay in the project during the implementation of strategies). In addition, some of the project's researchers and undergraduate nutritionists will participate as support in the measurement period. The brigade will work in each of the schools for approximately one week, starting with the intervention schools. It is expected that in 2 months, all the required information will be completed. The responsibilities will be distributed inside the brigade to optimize the time. The qualitative component will be implemented by different brigade personnel to ensure their specialization in qualitative methodologies. The project will count with one general field supervisor to ensure that the brigade personnel is advised and supported at all times.

Field staff will receive the appropriate training in interviewing techniques, ethical considerations, filling out specific questionnaires, training in the anthropometric measures, and blood pressure. One researcher will be trained in the SOFIT method. Only the standardized personnel with the specific techniques will be responsible for gathering the information.

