During the periods of strategy implementation, the project will have four people who will stay permanently in the locality for the duration of the intervention. A member of the project will be permanently in charge of implementing and monitoring the strategies at one of the community interventions schools, keeping direct contact with key actors. The same person will be a member of the health and nutrition committee of the school. In addition, monitoring activities will be carried out in the comparison schools, which will be systemized into indicators for the evaluation process. On the other hand, it is contemplated the support of nutritionists and other undergraduate professionals to support the elaboration of material, application of interventions, events, workshops, and measurements, with previous training and standardization.

Additionally, formative research will enrich the proposed strategies. This will be carried out with the support of personnel specialized in qualitative methodologies. Two people will be in charge of implementing the qualitative component, which will consist of non-participating observation, focus groups, and semi-structured interviews with children and key actors (parents, teachers, school principals, municipal authorities, and community leaders); to inquire about opinions, prejudices, and beliefs regarding the implementation of the guidelines that regulate food sales within school grounds. The same staff will be responsible for analyzing the information and determining the barriers and possible solutions to improve eating habits and encourage physical activity in the population (during the qualitative instruments' application, one more person will be supporting the research team). The focus group among children will be held inside the schools, working mainly with fifth and sixth-grade students. In addition, all teachers at each school will be invited to participate in a focus group that will be held at the school campus with the support of the principals. Semi-structured interviews will be conducted with children, parents, and teachers. The specialized staff in qualitative methodologies will personally arrange with each of the interviewees the day, time, and place where interviews will be held, supporting the interviewees' convenience.

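### Staff who deliver the programme may also measure observer-dependent outcomes in their own intervention schools, so bias can differ by arm after baseline

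*Protocol*

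**What the plan says.** Three parts of the protocol describe the field staff.

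- **Budget.** Two social service providers are "in charge of collecting quantitative information during the different stages, as well as implementing and evaluating the intervention".
- **Fieldwork logistics in evaluation periods.** Data collection in all three periods "will be organized with a single brigade of six people". For the evaluations "there will be two more people to complement the 6-member brigade and facilitate the collection of information". The same sentence then turns to the implementation phase: "while four members will stay in the project during the implementation of strategies". Project researchers and undergraduate nutritionists also help.
- **Strategy implementation.** During implementation "the project will have four people who will stay permanently in the locality for the duration of the intervention". Further, "A member of the project will be permanently in charge of implementing and monitoring the strategies at one of the community interventions schools", and "The same person will be a member of the health and nutrition committee of the school". The Summary says that a research team member takes charge of the strategies in each intervention school. Undergraduates may support both the intervention and the measurements.

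The schools in Villa Corona "will only be evaluated (control group"; between evaluations the project only monitors them.

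The stated safeguards are training, data collection by standardized personnel only, a general field supervisor, separate staff for the qualitative component, and a university laboratory for the blood work. None of them keeps implementers apart from the collection of the other quantitative outcomes.

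**The concern.** Many of the main outcomes in the Information analysis plan depend on how someone asks, watches, scores or encourages: belief, attitude and knowledge scores, food consumption, food availability, the number and quality of activity spaces, and endurance, speed and strength tests. If the assessor has spent months delivering the programme in that school, two things can happen. The assessor may score in line with what he or she hopes to see. The child, parent, teacher or vendor may answer or behave as this familiar person would wish.

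Food availability is a clear case. Under the proposed strategies, project staff watch compliance with the food-sale guidelines, report breaches to the principal and advise the sellers. The same staff could later take the food inventory at the same stall.

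No equivalent relationship exists in the control schools, so any such effect would be counted as an effect of the intervention.

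**Working it through.** The point rests on who measures what, so the check is mainly textual.

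**1. Do the roles overlap?** Yes. The Budget states it outright for the two providers. Fieldwork logistics states it for four brigade members: four of six, or four of eight if the two evaluation-period people come on top of the six. Strategy implementation also counts four permanent staff in the intervention locality.

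**2. Is the overlap confined to one arm?** The same brigade measures both arms. What exists only in the intervention schools is prior delivery of the programme there, with the familiarity that follows.

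**3. When does it arise?** The schedule table puts the baseline in October–November 2015 and strategy implementation from January 2016. The intermediate measurement is in September–October 2016 and the final one in May–June 2018. By that table the baseline is free of the implementer role and both later measurements are exposed. (The text above the table has the intervention beginning in September 2015; this check relies on the table.)

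**4. Where does it enter the estimate?** Assume the effect is read as the difference between arms in change from baseline. Let b be the mean shift caused by measurement in arm I or C, at baseline (0) or follow-up (t):

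bias = (b_I,t − b_I,0) − (b_C,t − b_C,0)

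For the part due to the assessor being that school's implementer, b_I,0 = 0 by step 3 and b_C,0 = b_C,t = 0 by step 2. So bias = b_I,t, which passes in full into the arm difference. The number of children does not appear, so a larger sample would not dilute it.

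**5. Which outcomes are exposed?**

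| Outcome | How obtained | Exposure |
|---|---|---|
| Belief, attitude and knowledge scores | Questionnaire | Yes |
| Food consumption | Interview and direct observation | Yes |
| Food availability in school | Registration form with food scale | Yes, partly through vendor behaviour |
| Quality of activity spaces | Staff judgement | Yes |
| Endurance, speed and strength | Staff-run, effort-dependent tests | Yes |
| Steps | Pedometer | Less |
| Glucose and lipids | Sampled and analysed by laboratory staff | Outside the point |
| SOFIT | One trained researcher | Not determinable; implementing role not stated |

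**6. Can existing staff cover a separation?** With one implementer barred in each intervention school, 6 − 1 = 5 brigade members remain for the rated instruments there. If a further member works across all three schools, 6 − 2 = 4 remain. If all four permanent staff implement in every school, 6 − 4 = 2 remain, or 8 − 4 = 4 if the two evaluation-period people are additional. The Summary and Strategy implementation point to about one implementer per school, so the first two cases are the likelier ones.

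**The case against.** The best defence is that the protocol never says who measures which school with which instrument, so it does not say that any implementer will rate his or her own school. Data are gathered only by standardized personnel under a field supervisor, training precedes each evaluation, and the coordinator and an operative lead answer for data quality. This stands in part: it limits random rater error and makes the point a risk. Standardization does not, however, remove expectation or familiarity tied to arm.

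Several stronger readings are tempting, and the documents do not support them.

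- *Observer bias acts only in the intervention arm.* Assessors know which municipality they are in, so expectation can act in control schools too. Only familiarity and rating one's own work are confined to one arm.
- *The data collectors are the committee members.* No section equates the two providers with the person on the school committee, and two providers are not reconciled with four permanent staff.
- *SOFIT is compromised.* It goes to one trained researcher and is not in the listed main outcomes.
- *The bias can be stated as a share of the effect the trial was sized to find.* The protocol gives no effect size, SD or intracluster correlation. Its 288 children (6 schools × 4 grades × 12) less 30% leave 201.6, or 100.8 per arm and 33.6 per school. Ignoring clustering, the detectable difference is (1.96 + 0.8416) × √(2/100.8) = 0.395 SD. Multiplying by √(1 + 32.6 × ICC) gives 0.45 SD at an assumed ICC of 0.01 and 0.64 SD at 0.05. Any share would divide an assumed shift by an assumed denominator.
- *No analysis can help.* With assessors crossed between schools and identified on the forms, a sensitivity check is possible, though not a full correction.

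**Conclusion.** The point holds as a design risk. The protocol gives overlapping staff both the implementation in intervention schools and the collection of quantitative outcomes, and it has no rule that separates the roles within a school. Observer and response bias can therefore differ by arm at the intermediate and final measurements and fall on the change from baseline, for outcomes that are interviewed, observed or staff-administered. Nothing in the protocol shows that such bias occurs or how large it would be, and no figure should be attached to it.

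The conclusion assumes that implementation follows the baseline, as in the schedule table, and that brigade members who stay on to implement also take part in later evaluations. The second is stated for the two providers and implied for the other staff. Field staffing is fixed in this protocol and is not a matter that a statistical analysis plan would be expected to settle. The change should be made because the weakness is avoidable at low cost.

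**What to change.** In Fieldwork logistics in evaluation periods and in Budget:

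- State that nobody who implements strategies in a school, including undergraduates who support the intervention there, collects interviewed, observed or effort-dependent outcomes in that school.
- Cover these instruments by a rota of the existing brigade and evaluation-period staff. Each assessor works in both intervention and control schools, with preference for people who have no implementing role.
- Let the school's own implementer handle logistics or instrument-read measures.
- Record assessor ID on every form, so that a sensitivity check by assessor is possible.
- State whether the SOFIT researcher also implements.
- Reconcile the two providers in Budget with the four permanent staff in the other two sections, and say whether the two evaluation-period people are within the six or additional.

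The cost is less flexible scheduling and some extra training on the rated instruments. If about one implementer is attached to each intervention school, no new posts are needed. Assessors will still know the municipality, and someone who implements in a sister school may still carry expectation, so the bias is reduced and not removed.
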